#### **8.4.6 Electrocardiograms (ECGs)**

NA

#### **8.4.7 ECOG**

NA

#### **8.4.8 Physical Examination**

NA

#### **8.4.9 Prior and Concomitant Medications and Procedures**

The following definition will be used to define prior and concomitant medications:

- Prior medications will include medications which stopped prior to the first dose of study drug.
- Concomitant medications are defined as medications that were started prior to first dose of study drug or at any time after the start of first dose of study drug and stopped prior to the discontinuation of study drug.

The reported medication term will be coded using the World Health Organization (WHO) Drug Dictionary in effect at the time of the analysis. The number and percentage of participants taking concomitant medications will be summarized by dose level/Cohorts and generic name, sorted in decreasing order of frequency. All reported prior and concomitant medications will be listed by subject.

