### 9.3. Concomitant Medications

Unless clinically indicated, subjects should avoid taking additional non-study medications that may interfere with study treatments. Any medication or vaccine, including over-the-counter or prescription medicines, vitamins, and/or herbal supplements that the patient is receiving at the time of enrolment or receives during the study must be recorded in the CRF along with:

- Reason for use
- Dates of administration including start and end dates
- Dosage information including dose and frequency

Details of prohibited medications are detailed in [Table 12](#) and [Appendix 6](#).

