#### 13.1.1. Demographic/Medical History

Demographic information will be collected at the Screening Visit. Standard demography parameters will include age, gender, and race/ethnicity (recorded in accordance with prevailing regulations). The screening visit will occur within 28 days prior to the first dose of study drug to confirm that the subjects meet the selection criteria for the study. The assessments to be conducted at screening are provided in [Table 8](#) (Schedule of Assessments for Dose Escalation and Dose Expansion). Medical and surgical histories will be obtained at the Screening Visit, along with a record of prior concomitant medications and/or procedures. Significant findings before the start of study drug will be recorded on the Medical History and Current Medical Conditions eCRF. A standard of-care clinical examination for MM and lymphoma, including assessment of B symptoms, will also be performed at the screening visit and at all disease assessments.

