#### 13.1.2. Prior and Concomitant Medications

Prior and concomitant medications include all prescription and nonprescription medications, vitamins, herbals (including medical marijuana), and transfusions.

All prior medications (including over-the-counter medications) administered 30 days before the first dose of study drug will be recorded. Any concomitant therapy administered to the subject during the course of the study (starting at the date of informed consent) until 30 days after the final dose of study drug will be recorded. Additionally, all diagnostic, therapeutic, or surgical procedures relating to malignancy should be recorded.

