### **17.3. Written Informed Consent**

Informed consent will be obtained, and protocol eligibility will be established during the Screening Visit. Informed consent will be obtained after the study has been fully explained to the subject and before the conduct of any screening procedures or assessments. For research biopsies a separate consent form will be provided for DLBCL subjects.

It is the responsibility of the Investigator to obtain written informed consent from each subject before any protocol-specific assessments and/or procedures are performed. All consent documentation must be written in the source documents, approved, used, and maintained in accordance with applicable regulations and GCP. If applicable, an ICF will be provided in a certified translation of the subject's local language.

Each Investigator will provide the Sponsor or its designee with a copy of the IRB/IEC approved ICF(s), and a copy of the IRB/IEC written approval, prior to the start of the study. Additionally, if the IRB/IEC requires modification of the sample subject information and the model ICF provided by the Sponsor, the documentation supporting this requirement must be provided to the Sponsor.

Each subject or the subject's legally authorized representative is requested to sign the approved ICF after the subject has received and read the written subject information and received an explanation of what the study involves, including but not limited to: the objectives, potential benefits and risk, inconveniences, and the subject's rights and responsibilities. The subject should be given the opportunity to ask questions and allowed time to consider the information provided. A copy of the ICF (subject information sheet and the ICF, as applicable) must be given to the subject or the subject's legally authorized representative.

Original, signed ICFs must remain in each subject's study file and must be available for inspection at any time.

The Sponsor reserves the right to delay initiation of the study at a site where the ICF(s) do not meet the standards of applicable regulations and ICH GCP.

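### The SAP's definition of concomitant medication leaves a drug started on treatment and still running at discontinuation in no class, so the one count-and-percentage table could be miscounted (minor)

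*SAP*

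**What the plan says.** SAP 8.4.9 gives two definitions. The first reads: "Prior medications will include medications which stopped prior to the first dose of study drug". The second calls a medication concomitant if it began before first dose, or "at any time after the start of first dose of study drug and stopped prior to the discontinuation of study drug". There is no third class, no rule for a drug still running at discontinuation, no rule for a missing stop date, and no statement that the classes exclude each other.

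The same section then sets the output: "The number and percentage of participants taking concomitant medications will be summarized by dose level/Cohorts and generic name". It also asks for a by-subject listing. Elsewhere SAP section 8 asks for Phase 1a listings, so this is the SAP's only count-and-percentage table.

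Protocol 13.1.2 sets what sites collect. Medications "administered 30 days before the first dose of study drug will be recorded", and the on-study part covers: "Any concomitant therapy administered to the subject during the course of the study (starting at the date of informed consent) until 30 days after". That window is counted from last dosing. Protocol 9.3 requires, for each medication: "Dates of administration including start and end dates".

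**The concern.** A concomitant-medication table should show what participants were taking while exposed to study drug. The SAP sentence adds a stop condition that works against this. A drug begun for a toxicity and continued past the end of treatment is plainly concomitant in the ordinary sense, yet it fails the condition because it had not ended by the time study drug was discontinued.

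The pattern is plausible in this trial. Protocol 7.5.1 and 7.5.2 describe managing toxicity with concomitant medication, interruption and discontinuation, alone or together, so a drug started for the event that ends treatment may well still be running at that point. This is an inference from the design; the documents hold no medication records.

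The sentence is also ambiguous, so two programmers could produce different tables from the same data. Concomitant-medication monitoring is listed among the Phase 1a primary safety endpoints (SAP section 3), and this table is the only place where the SAP summarises it.

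**Working it through.** The plan gives no figure to reproduce, and no sample-size or error-rate arithmetic applies. The check applies the definitions to each timing pattern.

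Inputs, all from SAP 8.4.9 unless stated:

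- P: the drug ended before first dose (prior).
- A: the drug began before first dose.
- B: the drug began on or after first dose. SAP 7.2 places first-dose-day starts here.
- C: the drug ended before discontinuation of study drug.

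In outline, the concomitant sentence has the form A or B and C, and it can be grouped in two ways:

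- Grouping 1: A or (B and C). The stop condition applies only to on-treatment starts.
- Grouping 2: (A or B) and C. The stop condition applies to every start.

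For illustration, put first dose on day 1 and both last dose and discontinuation on day 57. The SAP columns depend only on the order of events, not on these days. The last column applies the rule proposed under the fix, with a window ending 30 days after the final dose (57 + 30 = day 87).

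| Pattern (start, stop) | Grouping 1 | Grouping 2 | Proposed rule |
|---|---|---|---|
| Before first dose, before first dose (-20, -5) | prior and concomitant | prior and concomitant | prior |
| Before first dose, on treatment (-20, 20) | concomitant | concomitant | concomitant |
| Before first dose, ongoing at discontinuation | concomitant | **neither** | concomitant |
| Before first dose, after discontinuation (-20, 70) | concomitant | **neither** | concomitant |
| On treatment, on treatment (10, 20) | concomitant | concomitant | concomitant |
| On treatment, on the discontinuation day (10, 57) | **neither** | **neither** | concomitant |
| On treatment, ongoing at discontinuation | **neither** | **neither** | concomitant |
| On treatment, after discontinuation (10, 70) | **neither** | **neither** | concomitant |
| After discontinuation, within 30 days (60, 70) | neither | neither | concomitant, or shown separately if a shorter window is chosen |

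Three results follow.

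1. For a drug begun on treatment and not ended before discontinuation, A is false, B is true and C is false. Grouping 1 gives false or (true and false), which is false. Grouping 2 gives (false or true) and false, which is false. P is also false. The gap therefore does not depend on how the sentence is parsed.
2. For a baseline drug still running at discontinuation, A is true and C is false. Grouping 1 gives true and Grouping 2 gives false, so the parsing decides.
3. For a drug that ended before first dose, P, A and C are all true, so it meets both definitions under either grouping.

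Next, does other text repair this? SAP 7.2 settles only starts on the day of first dose. SAP 7.6 rules out imputation unless noted, so an ongoing drug is not given a stop date. Protocol 13.1.2 sets no stop condition, but it says what is recorded, not how records are classed for analysis. Protocol 14.2 gives precedence to the SAP on planned analyses. None of these changes the table above.

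**The case against.** The strongest reply is that this hardly matters. The study was terminated during escalation for business reasons, only selected analyses will be run, and nearly everything is listed. SAP section 1 says the SAP is to be read with the protocol, whose wording on concomitant therapy has no stop condition, so the intended meaning is fairly clear. Start and end dates are recorded, so any record can be reclassified, and the by-subject listing may still show every drug. The prior definition also assigns drugs that ended before first dose, so a sensible programmer would not count them twice.

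Most of this stands, and it sets the severity. It does not remove the defect. SAP section 1 also requires any departure from the SAP to be documented and justified in the study report. Following the text gives a wrong table, and quietly correcting it is an undocumented departure.

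Three stronger readings are tempting, and the documents do not support them.

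- A reader might infer that the SAP contradicts protocol 13.1.2 for drugs that ended between consent and first dose. That section is a recording window. It defines no analysis class, so there is no conflict of definitions.
- A reader might infer a bound on that overlap. Protocol 13.1.1 says: "The screening visit will occur within 28 days prior to the first dose of study drug". Protocol 17.3 says: "Informed consent will be obtained, and protocol eligibility will be established during the Screening Visit". Together these suggest that 1 to 28 of the 30 pre-dose recording days fall after consent. For dose escalation, however, protocol 7.1 and section 11 place screening within 28 days of signing consent. Consent can then precede day -30, and all 30 days can fall after it. The bound would in any case count days, not misclassified participants.
- A reader might infer that every drug begun after the last dose is unclassified. Discontinuation need not coincide with the last dose: it may be decided during an interruption. A drug begun after the last dose and ended before that decision meets the SAP's wording under both groupings.

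**Conclusion.** The concern holds as a minor wording defect. Read literally, SAP 8.4.9 puts a drug begun on treatment and not ended before discontinuation in neither class under both groupings. It treats a baseline drug still running at discontinuation inconsistently, and it lets a drug that ended before first dose meet both definitions. The table could therefore undercount the first group, possibly undercount the second, and overcount the third.

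The number of participants affected cannot be computed: the documents give no medication records and no safety-population size per dose level. A participant is lost from a generic-name row only if none of that participant's records of the drug qualifies, and is wrongly added only if every qualifying record ended before first dose.

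Because concomitant-medication monitoring is listed with the primary safety endpoints, a reader might infer that the safety or MTD conclusion is at risk. The documents do not support that: escalation and MTD selection use DLT counts, and no dose decision, test or estimate draws on this table. The finding assumes only that the definition is applied as written.

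**What to change.** Replace the two definitions in SAP 8.4.9 with the following.

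- Prior: ended before first dose.
- Concomitant: taken at any time from first dose to one stated end of window, whatever the start date. This includes drugs marked ongoing and drugs with no stop date, unless they can be shown to have ended before first dose.
- The two classes are mutually exclusive.

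For the end of the window, 30 days after the final dose matches what protocol 13.1.2 collects. It also keeps in the table any drug begun for a toxicity after the last dose, for example during an interruption from which dosing never resumes. If a shorter window is preferred, later starts should appear in a separate row or listing so that they are not lost.

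The cost is one revised SAP definition and one programming flag. No new data are needed. If the SAP is not revised, the rule actually used should be stated and justified in the study report, as SAP section 1 requires for any departure.

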#### **8.4.10 Subsequent Anticancer Therapy**

NA

## **9. PHARMACOKINETIC AND PHARMACODYNAMIC ANALYSIS**

### **9.1. Analysis of Pharmacokinetics**

Plasma concentrations will be listed based on the PK population.

### **9.2. Analysis of Pharmacodynamics**

No pharmacodynamic analysis will be conducted in this study.

